11.3 Statistical Methods

The primary endpoints for the study are related to safety and tolerability of infusion of daratumumab in AL amyloidosis with respect to infusion reactions.

Secondary endpoints include hematologic response rate of single agent daratumumab, organ responses with respect to cardiac biomarkers and proteinuria, and time to next treatment.

The Health Related Quality of Life, as reported in SF-36, will be an exploratory endpoint.

Statistical analysis will be based on all eligible subjects. Safety analysis population includes all enrolled subjects who received at least one dose of study drug. The safety analysis population will be used for evaluating subject characteristics, treatment administration, safety endpoints, and efficacy analyses.

There will be no formal statistical hypothesis testing applied in this study. Descriptive summary statistics will be used throughout. Data will be summarized primarily by administration time and aggregated across the first 8 weeks and 2 weeks after.

Continuous variables will be summarized by the number of non-missing observations, mean, standard deviation (SD), median, minimum and maximum.

Categorical variables will be summarized by the number of non-missing observations, frequencies and percentages.

All analyses will be performed using SAS® (SAS Institute Inc., Cary, North Carolina, U.S.) version 9.4 or higher.

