Infusion rates for daratumumab administration:

	Dilution volume	Initial rate (1 st hour)	Rate increment ^a	Maximum rate
First infusion	1000 mL	50 mL/hour	50 mL/hour every hour	200 mL/hour
Second infusion ^b	500 mL	50 mL/hour	50 mL/hour every hour	200 mL/hour
Subsequent infusion ^c	500 mL	100 mL/hour	50 mL/hour every hour	200 mL/hour

^a Consider incremental escalation of the infusion rate only in the absence of infusion reactions.

^b Use a dilution volume of 500 mL only if there were no Grade 1 (mild) or greater infusion reactions during the first 3 hours of the first infusion. Otherwise, continue to use a dilution volume of 1000 mL and instructions for the first infusion.

^c Use a modified initial rate for subsequent infusions (i.e. third infusion onwards) only if there were no Grade 1 (mild) or greater infusion reactions during a final infusion rate of ≥ 100 mL/hr in the first two infusions. Otherwise, continue to use instructions for the second infusion.

Daratumumab will be administered at the FDA-approved dose of 16mg/kg as an intravenous infusion. Weight from screening visit will be used for initial dosing and throughout treatment period but will be recalculated for weight change $\geq 10\%$. It will be administered weekly from weeks 1 to 8, followed by every 2 weeks from weeks 9 to 24, and then every 4 weeks thereafter until progression or unacceptable toxicities, for up to 24 months of total study therapy.

The first infusion of daratumumab (in 1000 mL) will be administered at an initial rate of 50 mL/hour to be escalated hourly by 50 mL/hour to a maximum rate of 200 mL/hour.

The second infusion of daratumumab will be administered in 500 mL if no grade 1 or greater reactions have occurred throughout the first 3 hours of the first infusion. The second infusion will be administered at an initial rate of 50 mL/hour to be escalated hourly by 50 mL/hour to a maximum rate of 200 mL/hour

The third and subsequent doses will be administered in 500 mL at a starting rate of 100 mL/hour to be escalated hourly by 50 mL/hour to a maximum rate of 200 mL/hour as long as no \geq Grade 1 infusion reactions occur during a final infusion rate of ≥ 100 mL/hr in the first two infusions.

Infusion reactions of any grade will lead to the temporary interruption or slowing of the infusion, as well as management of symptoms. Depending on the grade/severity of the reaction, this may require the permanent discontinuation of the drug.

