7.0 TREATMENT PLAN

Drug	Dose ^c	Frequency	Route of Administration
Daratumumab	16 mg/kg body weight	Weekly, weeks 1-8	IV infusion
Daratumumab	16 mg/kg body weight	Every 2 weeks, weeks 9-24 ^a	IV infusion
Daratumumab	16 mg/kg body weight	Every 4 weeks, week 25 ^b onwards, for up to 24 months of total study therapy	IV infusion

^a First dose of the every-2-week dosing schedule is given at week 9

^b First dose of the every-4-week dosing schedule is given at week 25

^c Weight from screening visit will be used for initial dosing and throughout treatment period but will be recalculated for weight change $\geq 10\%$.

Infusion rates for daratumumab administration

	Dilution volume	Initial rate (1 st hour)	Rate increment ^a	Maximum rate
First infusion	1000 mL	50 mL/hour	50 mL/hour every hour	200 mL/hour
Second infusion ^b	500 mL	50 mL/hour	50 mL/hour every hour	200 mL/hour
Subsequent infusion ^c	500 mL	100 mL/hour	50 mL/hour every hour	200 mL/hour

^a Consider incremental escalation of the infusion rate only in the absence of infusion reactions.

^b Use a dilution volume of 500 mL only if there were no Grade 1 (mild) or greater infusion reactions during the first 3 hours of the first infusion. Otherwise, continue to use a dilution volume of 1000 mL and instructions for the first infusion.

^c Use a modified initial rate for subsequent infusions (i.e. third infusion onwards) only if there were no Grade 1 (mild) or greater infusion reactions during a final infusion rate of ≥ 100 mL/hr in the first two infusions. Otherwise, continue to use instructions for the second infusion.

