10.0 CRITERIA FOR EVALUATION AND ENDPOINT DEFINITIONS

Patients will not be required to have a delta FLC of 40 mg/L for study entry as primary endpoint of the study is to evaluate safety and tolerability of the study drug. Hematologic responses will be assessed by other hematologic measures of disease including M-spike and presence of clonal plasma cells in the bone marrow. Organ responses will be assessed by changes in 24 hour protein excretion for patients with renal involvement; by changes in NT-proBNP for patients with cardiac involvement; and by changes in alkaline phosphatase levels and liver span for patients with hepatic involvement.

10.1 Toxicities:

Safety of the study drug will be assessed by using vital sign information in addition to data pertaining to the duration of therapy, interruption of therapy, routine laboratory assessments, and frequency and severity of AEs

10.2 Responses:

It is important to note that daratumumab is an IgGk monoclonal antibody that can be detected as an individual monoclonal band on SPEP and serum immunofixation electrophoresis (IFE). It can be confused with the endogenous IgG-k M-protein of the patient during IFE interpretation. Co-migration can introduce a bias in M-protein quantification and can also mask clearance of the patient's M-protein by IFE. For optimal M-spike monitoring, our laboratory specialist will be informed if a patient is receiving daratumumab.

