12.0 DATA AND SAFETY MONITORING PLAN

Toxicity and accrual monitoring will be performed on a routine basis by the study investigators as well as the multidisciplinary members of the Amyloid Center at Boston University, which has over 40 years' experience in the treatment of AL amyloidosis. Subjects will undergo toxicity assessment, performance status assessment and laboratory tests before each dose. Response assessment will be conducted every three months. The clinical status and laboratory reports of the study participants will be reviewed routinely by treating physicians. Dose modifications/interruptions or discontinuation will be implemented according to Section 8.

In addition, a Medical Monitor will be assigned to the study. The Medical Monitor must be a qualified clinician with relevant expertise, but no direct connection with the research, whose primary responsibility is to provide independent safety monitoring in a timely fashion. The PI will submit a

report to the Medical Monitor, at a minimum of once every 6 months, including a list of all adverse events and serious adverse events (regardless of relatedness). In addition, any unanticipated problems involving risks to participants or others and participant deaths within 30 days of study intervention will be reported to the Medical Monitor within 48 hours. The Medical Monitor is expected to provide a formal, unbiased written report evaluating individual and cumulative participant safety data when making recommendations regarding continuation of the study. Although the PI is responsible for assigning causality, the medical monitor will comment on whether or not (s)he is in agreement. Medical Monitor reports will must be submitted to the PI following each review (at a minimum of once every 6 months), which the PI will, in turn, submit to the IRB. Although there is no pre-determined criteria for early termination due to toxicity, the Medical Monitor and investigators will evaluate toxicities on a continuing basis, and will terminate the study early if toxicities exceed acceptable parameters. Each individual situation will be reviewed, and response data will be considered. The study will be stopped early if it appears that the benefit no longer outweighs the risks.

12.1 Interventional IIS Janssen Scientific Affairs Requirements for Safety Data Collection and Reporting

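### By-administration percentages for adverse events other than infusion reactions are not comparable across the weekly, 2-weekly and 4-weekly dosing phases

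*Combined protocol and SAP*

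**What the plan says.** Section 11.3 (Statistical Methods) gives the layout for the whole trial: "Data will be summarized primarily by administration time and aggregated across the first 8 weeks and 2 weeks after". For categorical data, which include whether an adverse event occurred, it says: "Categorical variables will be summarized by the number of non-missing observations, frequencies and percentages". There is no formal hypothesis testing. Nowhere do the documents give a person-time denominator, a fixed window after each dose, or a rule for assigning an adverse event to an administration.

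The schedule is in section 3.1: "It will be administered weekly from weeks 1 to 8, followed by every 2 weeks from weeks 9 to 24". Section 7.0 adds: "First dose of the every-4-week dosing schedule is given at week 25". Treatment runs "for up to 24 months of total study therapy".

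On collection, section 12.0 says: "Subjects will undergo toxicity assessment, performance status assessment and laboratory tests before each dose". The study calendar in section 9.0 agrees. Section 10.1 counts the "frequency and severity of AEs" among the safety data, so safety reporting goes beyond infusion reactions, although sections 1.0 and 11.3 tie the primary objective and endpoint to those reactions.

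**The concern.** A percentage per administration compares like with like only if each administration carries the same time at risk. For events that can start at any point between doses, such as infections, fatigue or diarrhea, the time at risk doubles at week 9 and doubles again at week 25. With the layout and statistics of section 11.3, a table of these events by dose number would climb in steps even if the risk per week never changed.

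At stake is how the later safety data are read. The trial has one arm, so no control group would show the same steps and expose them as a product of the schedule. A reader comparing early with late doses could not tell such a rise from cumulative toxicity.

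**Working it through.** The documents state no adverse-event rate per dose or per week, so there is no planned figure to reproduce. The rates below are assumptions, shown as a range.

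**Inputs from the documents**
- Dosing intervals w of 1, 2 and 4 weeks (sections 3.1 and 7.0).
- Maximum treatment of 24 months (section 3.1), taken here as 104 weeks.
- Enrolment of 25 patients (section 11.1).
- Infusion reactions can occur up to 48 hours after the infusion ends, with an incidence of 4% at infusions after the second, from myeloma data (section 3.1, safety).

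**Schedule.** Doses fall in weeks 1 to 8 (8 doses), weeks 9 to 23 by 2 (8 doses) and weeks 25 to 101 by 4 (20 doses), 36 in all. The phases last 8, 16 and 80 weeks, which is 8%, 15% and 77% of 104 weeks if nobody stops early.

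**Assignment.** Counting events from each dose to the next gives 1 week for doses 1 to 8, 2 weeks for doses 9 to 16 and 4 weeks for doses 17 to 36. Looking back from each pre-dose visit gives the same pattern one dose later: the visit at dose 9 looks back 1 week and the visit at dose 17 looks back 2.

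**Percentage per dose at a constant rate L per week:** P(at least one event) = 1 − exp(−L × w).

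| L per week | w = 1 | w = 2 | w = 4 | Ratio, w = 4 to w = 1 |
|---|---|---|---|---|
| 0.02 | 1.98% | 3.92% | 7.69% | 3.88 |
| 0.05 | 4.88% | 9.52% | 18.13% | 3.72 |
| 0.10 | 9.52% | 18.13% | 32.97% | 3.46 |
| 0.20 | 18.13% | 32.97% | 55.07% | 3.04 |
| 0.50 | 39.35% | 63.21% | 86.47% | 2.20 |

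The expected number of events per dose is L × w, so counts rise exactly 2-fold and then 4-fold at every rate.

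**Any adverse event, infusion reactions included.** With a fixed 4% reaction risk per dose, P = 1 − 0.96 × exp(−L × w). At L = 0.005 this gives 4.5%, 5.0% and 5.9% (ratio 1.32). At L = 0.02 it gives 5.9%, 7.8% and 11.4% (ratio 1.93). At L = 0.10 it gives 13.1%, 21.4% and 35.6% (ratio 2.71).

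**Infusion reactions alone.** The 48-hour window is shorter than the shortest interval of 7 days, so time at risk per dose is the same in all phases and the ratio is 1.0.

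**With a person-time denominator.** Expected events divided by patient-weeks is L in every phase, a ratio of 1.0. With 25 patients and no early stopping, exposure is 25 × 8 = 200, 25 × 16 = 400 and 25 × 80 = 2,000 patient-weeks. At L = 0.02 the expected events are 4, 8 and 40, or 0.08 per 4 patient-weeks in each phase.

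**The case against.** Four objections have force.

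- **The primary endpoint is unaffected.** A reader might infer that the primary safety analysis is distorted, since section 10.0 speaks of safety and tolerability of the drug in general. The documents do not support that. Sections 1.0 and 11.3 limit the primary objective and endpoint to infusion reactions, and a percentage per administration is the suitable display for those. This objection stands in full.
- **No assignment rule is stated.** Pre-dose assessment says when patients are asked about events, not how events are tabulated. The step pattern therefore follows from a natural reading, not from explicit text. That makes the point conditional. A fixed post-dose window would avoid the pattern, but the plan has none.
- **Not all other safety data are affected.** A reader might extend the point to laboratory values and vital signs. These are point measurements before a dose. With a constant underlying rate, the expected share abnormal at a visit does not depend on the time since the last visit, so the planned by-visit display does not distort them.
- **Nothing formal depends on it.** There is no hypothesis test, and the interim rule in section 11.2 uses the first 3 doses, all in the weekly phase. The Medical Monitor receives lists of all adverse events. No early-versus-late comparison is planned. The absolute numbers are also small: at 0.02 per week and all 25 patients treated, 25 × 0.0198 = 0.5 against 25 × 0.0769 = 1.9 patients per dose.

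The planned aggregate helps only in part. Over the first 8 weeks the interval is constant. The meaning of the added 2 weeks is unclear; if it is weeks 9 and 10, the aggregate covers 10 of about 104 weeks. None is specified for the 4-weekly phase.

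**Conclusion.** The concern holds for adverse events other than infusion reactions. Under the stated layout, percentages per dose for these events cannot be compared between dosing phases. At a constant rate, the 4-weekly figure exceeds the weekly one by about 3.9-fold at 0.02 per week, 3.5-fold at 0.1 and 3.0-fold at 0.2, and event counts differ 4-fold. The ratio nears 4 only for infrequent events. It is about 1.3 to 2.7 for any adverse event at rates of 0.005 to 0.10 per week once a 4% reaction risk per dose is included.

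This rests on three assumptions: events are assigned to doses over the whole inter-dose interval, the rate is constant, and it lies in the range shown. The severity is minor, because the primary endpoint, the interim rule and the sample size are untouched. What is affected is the descriptive reading of later toxicity.

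**What to change.** In section 11.3:

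1. Keep the by-administration tables for infusion reactions.
2. Assign every other adverse event to a dosing phase by its onset date: weeks 1 to 8, weeks 9 to 24, and week 25 onward.
3. In each phase, report the number of patients with at least one event and the events per patient-month of exposure, stating how a month is counted. Base comparisons between phases on the rate, because the phases differ in length. At a constant 0.02 per week, the chance of at least one event is 1 − exp(−0.02 × 8) = 14.8%, 1 − exp(−0.02 × 16) = 27.4% and 1 − exp(−0.02 × 80) = 79.8%.

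The cost is a paragraph of text and a second table layout. Duration of therapy is already listed among the safety data in section 10.1; onset dates must be available for all adverse events, not only those sent as case reports. Precision will be low with about 25 patients, as the 4 expected events in the weekly phase at 0.02 per week show. The rate removes the effect of interval length only. It does not correct for patients who leave treatment early under section 7.4.

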Subjects who are positive for Anti-HBc or Anti-HBs will undergo testing for hepatitis B DNA by PCR. Subjects with serologic findings suggestive of HBV vaccination (Anti-HBs positivity as the only serologic marker) and a known history of prior HBV vaccination do not need to be tested for HBV DNA by PCR. During and following study treatment, subjects who have history of HBV infection will be closely monitored for clinical and laboratory signs of reactivation of HBV as specified in the Time and Events Schedule (Section 9). Where required by local law, the results of HBV testing may be reported to the local health authorities

Management of Hepatitis B Virus Reactivation:

Primary antiviral prophylaxis is permitted as per local standard of care. Per protocol, HBV DNA testing by PCR is mandatory for subjects at risk for HBV reactivation. For subjects who are diagnosed with HBV reactivation while on treatment, study treatment should be interrupted until the infection is adequately controlled. If the benefits outweigh the risks, study treatment may be resumed with concomitant antiviral prophylaxis as per local standard of care. Consult a liver disease specialist as clinically indicated.

7.4 Criteria For Removal From Protocol Treatment:

- 7.4.1 Hematologic progression of disease.
- 7.4.2 Organ progression in the absence of hematologic response
- 7.4.3 Complete hematologic response, with continuation of the study drug per the discretion of the treating investigator
- 7.4.4 Unacceptable toxicity.
- 7.4.5 The patient may withdraw from the study at any time for any reason.
- 7.4.6 Development of overt multiple myeloma.
- 7.4.7 Completion of 24 months of daratumumab.

- 7.5 All patients will be followed until initiation of next treatment.

8.0 **TOXICITIES TO BE MONITORED AND DOSAGE MODIFICATIONS**

See Section 3.0 for potential toxicities associated with daratumumab. In all patients experiencing such toxicities, an attempt should be made to distinguish between drug toxicity, associated medical illness, or disease (amyloid)-related symptomology.

Dose delay is the primary method for managing daratumumab-related toxicities.

Infusion-related reactions:

Infusion reactions of any grade will lead to the temporary interruption or slowing of the infusion, as well as management of symptoms. Depending on the grade/severity of the reaction, this may require the permanent discontinuation of the drug.

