11.0 STATISTICAL CONSIDERATIONS

11.1 Sample Size Estimation

Estimated patient accrual and trial duration: The study will be designed as a single armed phase II trial, in which the response in 20 evaluable patients will be determined, with 25 patients enrolled to ensure that 20 are evaluable

Completion of accrual will be expected in ~2 years, with an additional year of monitoring and follow up after the last patient is enrolled.

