11.3 Handling of Missing Data

Data will be analyzed as recorded in the database. No imputation of missing values will be performed unless indicated otherwise.

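### Time to next treatment has no time-to-event method; the only numeric summary in section 11.3, if applied to it, leaves out every patient who has not started a new therapy

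*Combined protocol and SAP*

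**What the plan says.** Section 1.4 lists time to next treatment as a secondary objective. Section 11.3 (Statistical Methods) repeats it among the secondary endpoints: "organ responses with respect to cardiac biomarkers and proteinuria, and time to next treatment". Section 10.0, which holds the endpoint definitions, covers hematologic and organ response but not this endpoint.

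On method, section 11.3 says "Descriptive summary statistics will be used throughout" and rules out formal hypothesis testing. It then gives one rule for numeric data, "Continuous variables will be summarized by the number of non-missing observations, mean, standard deviation (SD), median, minimum and maximum", and one for categorical data (counts and percentages). The second section numbered 11.3 (Handling of Missing Data) adds "No imputation of missing values will be performed unless indicated otherwise". Nothing is indicated otherwise for this endpoint.

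On follow-up, section 7.5 says "All patients will be followed until initiation of next treatment". Section 11.1 gives the expected timetable: "Completion of accrual will be expected in ~2 years, with an additional year of monitoring and follow up after the last patient is enrolled". No section states a data cut-off for the endpoint, a censoring rule, a rule for death before next therapy, or an estimator.

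**The concern.** A patient who has not started a new therapy has no observed time to next treatment. A summary of non-missing values therefore covers only patients who have already needed another therapy. It omits those still doing well without one, and those who died before one was started. Section 11.3 makes every dosed patient the population for efficacy analyses, but this summary would describe a subset selected by outcome.

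In a single-arm study with no testing, the descriptive estimate is the result. An analyst who applies section 11.3 literally and one who uses Kaplan-Meier would report different medians from the same data. Unless the method is stated, a reader could not tell which quantity was reported. Death before next therapy needs its own rule because it changes what the median means.

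**Working it through.** The plan gives no figure for this endpoint, so there is nothing to reproduce. The check asks what the non-missing summary returns when the truth is known.

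**Inputs from the plan.** 25 patients enrolled; accrual over about 24 months; one further year expected (section 11.1).

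**Assumptions, not in the plan.** Time to next treatment T is exponential with median m (6 or 24 months). Accrual is uniform, so follow-up F is uniform on (a, a + 24), where a is the number of months from last enrolment to cut-off. T and F are independent.

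**Share of patients with a value, no deaths.** With λ = ln 2 / m and a = 12:

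P(T ≤ F) = 1 − (e^(−12λ) − e^(−36λ)) / (24λ)

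- m = 6: 1 − (0.2500 − 0.0156)/2.773 = 0.915, about 23 of 25.
- m = 24: 1 − (0.7071 − 0.3536)/0.6931 = 0.490, about 12 of 25.

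**Median of the non-missing times, no deaths.** An observed time has density proportional to f(t)·P(F ≥ t). The second factor falls with t, so observed times are systematically shorter than T. Solving for the median numerically:

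| True median | a = 12 | a = 36 | a = 60 |
|---|---|---|---|
| 6 months | 5.30 (12% short) | 5.95 (1% short) | 6.00 (under 1% short) |
| 24 months | 9.73 (59% short) | 16.13 (33% short) | 19.84 (17% short) |

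**Adding deaths.** Assume time to death D has a median of 60 months, either with constant hazard or clustered early (Weibull shape 0.5). Observed times now have density proportional to f(t)·P(F ≥ t)·P(D ≥ t). Take the target as time to next treatment or death. Its median x solves x/m + (x/60)^k = 1, with k = 1 or 0.5.

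- m = 24, k = 1: x = 1/(1/24 + 1/60) = 17.14.
- m = 24, k = 0.5: x = 12.88 (0.537 + 0.463 = 1).

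Non-missing median against that target, true m = 24:

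| Death pattern | Target | a = 12 | a = 36 | a = 60 | Complete follow-up |
|---|---|---|---|---|---|
| Constant hazard | 17.14 | 8.93 (48% short) | 20% short | 8% short | 17.14 (no error) |
| Early-clustered | 12.88 | 8.68 (33% short) | 6% long | 25% long | 18.19 (41% long) |

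For m = 6 at a = 12, the results are 4.94 against 5.45 (9% short) with constant hazard, and 4.72 against 4.38 (8% long) with early-clustered deaths.

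**The death rule alone.** For m = 24 with constant death hazard, the median is 17.1 months as a composite and 24 if death is censored. As a competing event, cumulative incidence is (17.14/24)·(1 − 2^(−t/17.14)), which reaches 50% at t = 29.8 months.

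**Does the remedy work?** In 8,000 simulated trials of 25 patients at a = 12, the typical Kaplan-Meier median without deaths was 6.0 and 24.0 for true medians of 6 and 24 (not reached in 0% and 22% of trials). With constant-hazard deaths, the typical composite median was 5.4 and 17.2 (not reached in 0% and 4%), against targets of 5.45 and 17.14.

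**The case against.** The strongest reply is that the plan is silent here, not wrong. Section 11.3 never classes time to next treatment as a continuous variable. A Kaplan-Meier median is itself descriptive, so a commitment to descriptive statistics does not exclude it. Censoring is not imputation, so the missing-data rule does not bar it either. This stands as far as it goes: a reader might infer that the plan orders patients without new therapy to be dropped, and the text does not say so. It does not remove the concern. No other method is given, and Kaplan-Meier chosen later would not be pre-specified.

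The second reply concerns size, and it also stands. The largest shortfalls assume a cut-off 12 months after last enrolment. Section 11.1 offers that year as an expectation, not a data lock, while section 7.5 follows patients until next treatment. A reader might infer that the reported median must be too short. That holds only with deaths ignored and some patients still without new therapy at the cut-off.

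A reader might also see a contradiction between the further year in section 11.1 and therapy "for up to 24 months of total study therapy" in section 7.0. An expected duration and a maximum do not contradict each other. The missing start point is likewise a gap in detail, probably a modest one, since efficacy is analysed in dosed patients and most screening tests fall within 28 days of first dose.

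**Conclusion.** The concern holds in a limited form. The plan names a time-to-event endpoint and supplies only a summary of non-missing values, which does not suit it. If that summary is used, patients without a new therapy are left out.

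The size cannot be fixed from the documents, which give no expected time to next treatment, death rate or cut-off. Under the stated assumptions, the gap is small when next treatment comes early and large when about half the patients are still without one. It shrinks as follow-up lengthens. Measured against time to next treatment or death, it can be zero or change sign. The true medians, the 60-month death median and the exponential and Weibull forms are all illustrative.

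No decision rule rests on this endpoint. The point is worth fixing because it is cheap and because an unlabelled median could mean several different things.

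**What to change.** In section 11.3, replace the non-missing summary for this endpoint with a Kaplan-Meier analysis from first dose in all dosed patients. Censor patients alive without new therapy at last contact. Report the median with a 95% confidence interval, or state that it was not reached. Pre-state whether death before next therapy is an event in a composite or a competing event, with cumulative incidence in the latter case. State the data cut-off used, and report how many patients are then still without a next therapy.

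The cost is a few sentences and a standard procedure in the SAS version already specified. No additional patients are needed, and the primary safety analysis does not change.

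### Section 11.3 plans no confidence intervals for the infusion-reaction and response proportions, and no method that handles censoring for time to next treatment

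*Combined protocol and SAP*

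**What the plan says.** Section 11.1 (Sample Size Estimation) plans a single-arm study in which "the response in 20 evaluable patients will be determined, with 25 patients enrolled to ensure that 20 are evaluable". It gives no target rate, power or interval width.

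Section 11.3 (Statistical Methods) sets the endpoints. On the primary: "The primary endpoints for the study are related to safety and tolerability of infusion of daratumumab in AL amyloidosis with respect to infusion reactions". On the secondary: "Secondary endpoints include hematologic response rate of single agent daratumumab, organ responses with respect to cardiac biomarkers and proteinuria, and time to next treatment".

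The same section defines the population: "Safety analysis population includes all enrolled subjects who received at least one dose of study drug". It uses that population for efficacy as well as safety. It then states "There will be no formal statistical hypothesis testing applied in this study" and "Descriptive summary statistics will be used throughout".

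Two summary rules follow. For proportions: "Categorical variables will be summarized by the number of non-missing observations, frequencies and percentages". For continuous variables the rule lists the non-missing count, mean, SD, median and the two extremes. Nothing specific is said about time to next treatment. Neither Section 11 nor any other part of the document contains a confidence interval or precision statement.

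**The concern.** A single-arm study of 20 to 25 patients with no test and no sample-size rationale can still estimate rates. Its value then depends on how precisely it does so, and this plan quantifies precision neither at the design stage nor at reporting.

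The omission matters most where few or no events are likely. Section 3.1 cites myeloma experience in which individual severe reactions each occurred in under 2% of patients. Zero severe infusion reactions is therefore a realistic outcome here, and a table entry of 0% gives no hint of how high the true rate could be. For response, a percentage near the 29% myeloma figure cited in Section 2.0 would carry an interval tens of percentage points wide.

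Time to next treatment raises a separate problem of validity, not only of presentation. A patient with no next treatment by the end of follow-up has no event time. Summaries of non-missing values either leave that patient out or need some date put in place of the event.

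**Working it through.** **Inputs.**
- 20 evaluable and 25 enrolled; about 2 years of accrual and about 1 further year of follow-up after the last enrolment (Section 11.1).
- Safety denominator is all dosed patients, so up to 25 (Section 11.3).
- Myeloma reference rates: any-grade infusion reaction 46% at first infusion, and severe reactions under 2% each (Section 3.1); hematologic response 29% (Section 2.0).
- Treatment for up to 24 months (Section 7.0); follow-up until next treatment (Section 7.5).

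**The plan's own figure.** The 20 cannot be derived, because no rate, power or precision is given. The step to 25 can be reproduced: 20 / (1 − 0.20) = 25. The 20% non-evaluable rate is implied, not stated.

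**Zero events.** The exact two-sided 95% upper limit is 1 − 0.025^(1/n).
- n = 25: 1 − 0.025^(1/25) = 13.7%.
- n = 20: 1 − 0.025^(1/20) = 16.8%.

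Other methods give upper limits of similar size:

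| Method | n = 25 | n = 20 |
|---|---|---|
| Exact, two-sided 95% | 13.7% | 16.8% |
| Wilson, two-sided 95% | 13.3% | 16.1% |
| Rule of three (3/n) | 12.0% | 15.0% |
| Exact, one-sided 95% | 11.3% | 13.9% |

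**Chance of seeing no events.** This is (1 − p)^n for true rate p.
- p = 5%: 0.95^25 = 27.7%; 0.95^20 = 35.8%.
- p = 10%: 0.90^25 = 7.2%; 0.90^20 = 12.2%.

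So a true rate of 5% would produce a clean table in more than a quarter of such studies.

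**Non-zero counts.** The Clopper-Pearson limits for x events are the 0.025 quantile of Beta(x, n − x + 1) and the 0.975 quantile of Beta(x + 1, n − x).

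| Count | Percentage | Exact 95% interval |
|---|---|---|
| 1/25 | 4% | 0.1% to 20.4% |
| 7/25 (near the cited 29% response) | 28% | 12.1% to 49.4% |
| 6/20 (same, if 20 are analysed) | 30% | 11.9% to 54.3% |
| 12/25 (near the cited 46% any-grade reactions) | 48% | 27.8% to 68.7% |

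**Time to next treatment.** If accrual takes 24 months and follow-up ends 12 months after the last enrolment, a patient enrolled in month m of accrual has 24 + 12 − m months of follow-up. That is under 24 months whenever m exceeds 12. A patient enrolled in the second year could therefore still be on study drug when follow-up ends, with no next treatment to record. If such patients are left out, the summary covers only those whose event came early. If their last follow-up date is entered as though it were the event, their times are cut short. Either way the result is biased downward.

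**The case against.** The strongest reply is that nothing is lost. Section 11.3 requires the non-missing count and the frequency as well as the percentage, and an exact interval depends only on a numerator and a denominator. Any reader could compute it. The study is openly descriptive, and no decision in the plan uses the final percentage: the interim rule in Section 11.2 works on counts, and Section 12.0 leaves later safety review to the Medical Monitor and investigators. This stands. The missing intervals are a gap in planned reporting. They do not bias the proportions, and adding them changes no estimate or stopping step. A descriptive plan does not exclude them, however, since an interval is an estimate and not a test.

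A reader might infer several stronger claims that the documents do not support:
- That percentages will be reported bare, or that the data could not show which true rates they are compatible with. Counts and denominators are reported.
- That tolerability will be judged against the myeloma rates. Those rates are background; Section 11.3 plans no comparison and sets no benchmark.
- That 0% any-grade reactions is the danger. With 46% cited at first infusion, zero is implausible there. The zero-event point concerns severe reactions.
- That 16.8% is the safety limit in general. It applies to safety only if 20 patients are dosed; with all 25 dosed the limit is 13.7%.
- That response is a primary endpoint. It is secondary.

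On time to next treatment, one could answer that Section 7.5 follows every patient until the next treatment starts, so nobody is censored. That would require follow-up without a limit, whereas Section 11.1 expects about one year after the last enrolment. It is also true that Section 11.3 never says this endpoint will be treated as an ordinary continuous variable. But that is the only summary it offers that could be applied to a time.

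**Conclusion.** The point holds. The plan has no interval for its primary or response proportions and no stated precision for its sample size. At 20 to 25 patients this leaves unreported an upper limit of 13.7% behind a zero count (25 dosed), and an interval of about 37 percentage points around 7/25 (49.4 − 12.1 = 37.3). These figures assume exact two-sided 95% limits and illustrative counts; a one-sided 95% limit for zero events would be 11.3% at n = 25.

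The consequence differs between the two parts. For the proportions it is one of presentation: the study remains valid, but its main result would carry no planned statement of uncertainty. For time to next treatment it is a bias toward shorter times. The size of that bias cannot be computed, because the documents do not say how many patients will lack a next treatment at the end of follow-up.

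**What to change.** Add to Section 11.3:
- Exact (Clopper-Pearson) two-sided 95% confidence intervals for the proportion of patients with any-grade and with Grade 3 or higher infusion reactions, at the first infusion and overall, with all dosed patients as the denominator.
- The same intervals for hematologic, cardiac and renal response, with the denominator stated. Section 11.1 speaks of evaluable patients while Section 11.3 assigns efficacy to all dosed patients, so the text should say which is meant.
- A Kaplan-Meier analysis of time to next treatment with a 95% interval, censoring patients without a next treatment at last follow-up.

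One sentence in Section 11.1 giving the interval width that 20 or 25 patients provide would supply the missing precision.

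The cost is minor SAP wording and standard SAS output. No visit, procedure, treatment or patient number changes. The reported results will look less precise.
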